#### 4. Barriers to acquisition of ivabradine.

Reasons for not obtaining ivabradine will be summarized by randomization arm over time as classified in the case report form. Frequencies and percentages of the classified reasons will be presented for each visit and overall. Results will be presented as descriptive summaries.

### **10 CLINICAL EVENTS**

The following clinical events occurring within 180 + 14 days will be summarized by randomization arm. The summaries will be presented as incidences and rates.

The clinical events include:

- 1) Worsening HF defined as hospital admission for worsening signs and/or symptoms of HF or receiving unplanned intravenous (IV) diuretics for HF as an outpatient.
- 2) HF hospitalization
- 3) All-cause hospitalization
- 4) All-cause mortality
- 5) Composite of all-cause mortality and HF hospitalization

Incidences of the events will be tabulated by randomization arm and differences between the randomization arms will be tested using the Chi-square test.

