### **13 STATISTICAL CONSIDERATIONS**

#### **13.1 Data Collection Windows and Conventions**

Data will be presented according to the schedule of assessments in the study protocol. The possible visits and windows are baseline, Day 7-14 post discharge, 6 weeks post-discharge (42±14 days), 90 days post-discharge (±7 days), and 180 days post-discharge (±14 days). If participants missed their scheduled window, data collected from clinic visits and entered in the EDC system will be used if clinic visits occurred within 60 days of the assessment window.

Heart rate obtained from ECG assessment is the primary data source. If, however, ECG assessment was not performed, heart rate results from vital signs collected during the scheduled visit or clinical visit close to the visit window will be used.

For participants who are lost to follow-up, the latest date available is used as date of last contact for the purpose of determining their vital status. Lost to follow-up participants whose survival status are ascertained beyond the study period will be censored at 194 days (180 +14). Those whose last contact date falls within the study period will be censored at their date of last contact for any time to event analysis.

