## 7. Summary of clinical events

### a) All-cause mortality

Death is obtained from the DEATH data

If DEATH.DTHDT is not missing then DEATH=1; else if participant is assessed at any time point, DEATH=0.

Restrict deaths to within 194 days of discharge. (non-missing DEATH.DTHDT – PATIENT.DISDT  $\leq$  194).

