### b) Worsening heart failure unique per participant

Worsening heart failure is defined as hospital admission for worsening signs and/or symptoms of HF or receiving unplanned intravenous (IV) diuretics for HF as an outpatient is obtained from hospitalization data (REHOSP) and ER/Clinic Visits (ERCLIN) data sets.

If REHOSP.RELHF=1 or ERCLIN.ERIVTMT=1 then Worsening heart failure =1; else if participant is assessed at any time point, worsening heart failure =0.

Restrict HF hospitalizations or ER visits for unplanned IV diuretics to within 194 days of discharge. (non-missing REHOSP.HOSPDT – PATIENT.DISDT  $\leq$  194) and (ERCLIN.ERVISDT- PATIENT.DISDT  $\leq$  194).

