### c) HF hospitalization unique per participant

HF hospitalization is obtained from the hospitalization data (REHOSP),  
If REHOSP.RELHF=1 then heart failure hospitalization=1; else if participant is assessed  
at any time point, heart failure hospitalization=0.  
Restrict HF hospitalizations to within 194 days of discharge  
(non-missing REHOSP.HOSPDT – PATIENT.DISDT <= 194).

- d) All-cause hospitalization unique per participant  
All-cause hospitalization is obtained from the hospitalization data (REHOSP).  
If REHOSP.HOSPDT is not missing then all-cause hospitalization =1; else if participant  
is assessed at any time point, all-cause hospitalization=0.  
Restrict all-cause hospitalizations to within 194 days of discharge  
(non-missing REHOSP.HOSPDT – PATIENT.DISDT <= 194).
- e) Composite endpoint of mortality or HF hospitalization  
If DEATH (see ( a) above) =1 or HF hospitalization (see (c) above) =1 then  
Composite endpoint =1;  
Else if both are =0 then Composite endpoint=0.  
Event is restricted to within 194 days of discharge per component parts.

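### Clinical events: participants seen once and then lost or withdrawn count as event-free to day 194, so crude incidences are too low and unequal early loss creates a small false difference between arms

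*SAP*

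**What the plan says.** SAP section 10 sets the window: "The following clinical events occurring within 180 + 14 days will be summarized by randomization arm". It lists worsening HF, HF hospitalization, all-cause hospitalization, all-cause mortality, and the composite of death and HF hospitalization. On reporting it says "The summaries will be presented as incidences and rates", without defining person-time or a test for the rates. On comparison it says "Incidences of the events will be tabulated by randomization arm and differences between the randomization arms will be tested using the Chi-square test".

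Appendix 1 item 7 derives the indicators. A dated event within 194 days of discharge is coded 1. For death the alternative is "else if participant is assessed at any time point, DEATH=0", and for worsening HF it is "else if participant is assessed at any time point, worsening heart failure =0". HF hospitalization and all-cause hospitalization follow the same pattern, and the composite is 0 when both its components are 0. Nothing requires the assessment to be after baseline or near day 194.

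SAP 13.1 has a rule for incomplete follow-up. Participants lost to follow-up whose last contact falls within the study period "will be censored at their date of last contact for any time to event analysis". Those whose survival status is known beyond the study period are censored at day 194. No time-to-event analysis of the clinical events is specified. The only one in the SAP is time to ivabradine discontinuation, in section 11.

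**The concern.** A participant who leaves at week 2 adds a full 194 days of apparent freedom from death and hospitalization to the denominator, although nobody observed most of that time. The arm that loses more people early looks safer.

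Two features make this more than theoretical. First, protocol 11.1 provides only limited data on participants who discontinue early. The items it lists include ivabradine-related serious adverse events but not hospitalization or worsening HF, so a 0 after early exit may mean that the event was never collected. Second, protocol 7.4 brings the final-visit activities forward to the time a subject stops treatment. Ivabradine treatment is meant to be concentrated in one arm of this open-label trial, so follow-up could be cut short unequally.

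At stake are the SAP's only between-arm comparisons of death and hospitalization.

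**Working it through.** **The plan's own figure.** The documents state no event risk, loss rate or power for the clinical events. The only sizing for a binary comparison is 35% versus 50% ivabradine use with 85% power (protocol 10.2). It reproduces: 207 per arm with continuity correction, 414 in total, and 414 / 0.92 = 450. It has no bearing on the clinical events.

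**Inputs**
- Window: 194 days from discharge (SAP 10 and Appendix 1).
- Enrolled: 104 (SAP 2.3). I assume 52 per arm.
- Event risk by day 194: not given, so I assume 30%, with other values below. For death, protocol 1.1 gives 20–30% one-year mortality.
- Early loss: not given. I assume 5% in one arm and 15% or 25% in the other.
- Constant hazard; loss independent of events.

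**Expected crude incidence.** Let R be the true 194-day risk, L the fraction with early loss, and loss times uniform over 0–194 days. Events before loss are still recorded. The chance of this among those lost is

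m = 1 − R / (−ln(1 − R)).

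The crude incidence is (1 − L)R + Lm = R − L(R − m).

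For R = 0.30: −ln(0.70) = 0.3567; m = 1 − 0.30/0.3567 = 0.159; R − m = 0.141.
- L = 5%: 0.300 − 0.05 × 0.141 = 29.3%
- L = 15%: 0.300 − 0.15 × 0.141 = 27.9%
- L = 25%: 0.300 − 0.25 × 0.141 = 26.5%

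The true difference is zero. The false difference is 1.4 points (5% vs 15%) or 2.8 points (5% vs 25%).

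**Against sampling error.** SE of a difference at 52 per arm = √(2 × 0.3 × 0.7 / 52) = 9.0 points. The bias is 1.4/9.0 = 0.16 to 2.8/9.0 = 0.31 standard errors.

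**Death alone.** With constant hazard, one-year mortality of 20% gives 1 − 0.8^(194/365) = 11.2%, and 30% gives 17.3%. The same formula gives R − m = 0.055 and 0.084. Loss of 5% vs 25% then yields 0.20 × 0.055 = 1.1 points and 0.20 × 0.084 = 1.7 points.

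**Sensitivity to timing.** Suppose everyone is seen by day 14 and loss follows. With 5% vs 25% loss:

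| True risk, both arms | Loss uniform, days 14–194 | All loss at day 14 |
|---|---|---|
| 30% | 2.6 points | 5.5 points |
| 40% | 3.4 points | 7.3 points |

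With equal 10% loss and 40% risk there is no false difference, but both arms read 38.3%.

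**Effect on the test.** Simulation under no treatment effect (40% risk, loss uniform over days 14–194, 3,000 runs):

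| Per arm | Loss | Chi-square rejects | Log-rank rejects |
|---|---|---|---|
| 52 | 10% vs 10% | 6.1% | 5.3% |
| 52 | 5% vs 25% | 6.8% | 4.9% |
| 225 | 5% vs 25% | 11.3% | 4.9% |

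Monte Carlo error is about 0.4 points (√(0.05 × 0.95 / 3000)). In these runs Kaplan-Meier with censoring at loss recovered 40% in both arms to within about 0.2 points.

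**The case against.** **Low stakes.** The clinical events are not among the endpoints in SAP 2.5, and protocol section 9 treats them as additional data. SAP 13.6 makes analyses outside the listed endpoints exploratory, without p-values. This stands, and it limits the severity. It also exposes a conflict, because section 10 prescribes tests that 13.6 rules out. Dropping the tests would not correct the incidences.

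**Small effect, assumed inputs.** This stands. The expectation in SAP 13.5 of more than 10% missing data concerns day-180 heart rate, KCCQ and PGA, not event ascertainment. For lost participants whose survival is later confirmed, coding death as 0 is correct.

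**Rates may mean person-time.** Possibly, which would partly address unequal follow-up. As written they are undefined, and the comparison rests on incidences.

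**Kaplan-Meier needs non-informative censoring.** This is doubtful if open-label dropout differs by arm. But the present coding assumes that no lost participant has an event after leaving, which is harder to defend.

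A reader might infer two stronger points that the documents do not support:
- *That the crude proportions ignore death as a competing event.* With complete follow-up, a fixed-window proportion that counts a death without hospitalization as not hospitalized is exactly what the cumulative incidence function estimates. Competing risk becomes an issue only once censoring is introduced.
- *That a death after randomization but before discharge is coded as no death.* The instruction is "Restrict deaths to within 194 days of discharge", applied to a non-missing death-minus-discharge expression. A death dated before a recorded discharge gives a negative difference and passes. It would be dropped only if the discharge date were blank and the non-missing condition applied to the difference rather than to the death date. The documents settle neither. The wording needs clarifying, but no uncounted death is shown.

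**Conclusion.** The point holds as a modest analysis weakness. The coding treats unobserved time as event-free, which understates incidence in both arms whenever follow-up is incomplete and biases the comparison when early loss differs by arm.

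Under an assumed 30% risk and uniform, non-informative loss of 5% versus 15–25%, the false difference is 1.4–2.8 points, or 0.16–0.31 standard errors at 52 per arm. Very early loss or higher risk raises it, up to 7.3 points in the worst case tried. Equal loss removes the difference but not the understatement. At 104 participants the extra false-positive risk is small, so the main harm is to the reported incidences and differences. The true size depends on event risks and loss by arm, which the documents do not give. This is a cheap improvement rather than a threat to the trial's conclusions.

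**What to change.** Amend SAP section 10 and Appendix 1 item 7 together:

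1. Keep the crude counts by arm, and report how many participants in each arm were followed to the end of the window.
2. Add 194-day cumulative incidence by arm, with a confidence interval for the difference. Use Kaplan-Meier for death and the composite. Use the cumulative incidence function with death as a competing event for worsening HF and both hospitalization outcomes, so that the new censoring does not mishandle deaths.
3. Censor at last contact as in SAP 13.1, and extend that rule explicitly to withdrawals, since it now names only participants lost to follow-up.
4. Keep the discharge-anchored window; correcting the loss bias does not require a different clock. State that any death after randomization and before discharge counts as an event.
5. Define the rates in section 10, or delete the word.
6. Reconcile section 10 with 13.6. Either drop the p-values, or list the clinical events as an exception and use log-rank (death, composite) and Gray's test (the non-fatal events).

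The cost is SAP wording and a little programming. Event and discharge dates are already in the derivations, and the last-contact date is defined in 13.1. The estimates will rely on non-informative censoring, which the report should state.

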## 11 COMPETING RISK ANALYSIS OF DEATH

Participants are at risk of dying before the final visit, and thus death is a competing risk to ivabradine use. In order to account for participants who die prior to the 180 day visit, a competing risk analysis of time to ivabradine discontinuation will be conducted. Participants who die during the study will be coded separately from those who discontinue ivabradine use. The analysis will be performed using the cumulative incidence function (CIF) method with death as an additional censoring variable. The Gray's test (Gray, 1988) will be used to evaluate hypothesis of equality of the cumulative incidence functions.

### **13 STATISTICAL CONSIDERATIONS**

#### **13.1 Data Collection Windows and Conventions**

Data will be presented according to the schedule of assessments in the study protocol. The possible visits and windows are baseline, Day 7-14 post discharge, 6 weeks post-discharge (42±14 days), 90 days post-discharge (±7 days), and 180 days post-discharge (±14 days). If participants missed their scheduled window, data collected from clinic visits and entered in the EDC system will be used if clinic visits occurred within 60 days of the assessment window.

Heart rate obtained from ECG assessment is the primary data source. If, however, ECG assessment was not performed, heart rate results from vital signs collected during the scheduled visit or clinical visit close to the visit window will be used.

For participants who are lost to follow-up, the latest date available is used as date of last contact for the purpose of determining their vital status. Lost to follow-up participants whose survival status are ascertained beyond the study period will be censored at 194 days (180 +14). Those whose last contact date falls within the study period will be censored at their date of last contact for any time to event analysis.

### **13.2 General Analysis Conventions/Rules**

All analyzed continuous variables will be summarized using descriptive statistics including number of observations, mean, standard deviation, minimum, 25th percentile, median, 75th percentile, and maximum. All analyzed categorical variables will be summarized using frequency counts and percentages. Percentages are calculated out of non-missing values unless stated otherwise. Comparisons of continuous (or discrete ordered) variables between randomization groups will generally be tested using the Wilcoxon rank sum test. For the secondary endpoint (change from baseline of the measures), analyses will be conducted using the general linear model approach. For comparisons over more than 2 time points, when appropriate, mixed effects models will be used to account for correlation within participant observations and assess time-by-treatment interactions (see Appendix 2 for details). Tests of binomial outcomes between randomization groups will generally be done with a Chi-square statistic. Tests of treatment effects will generally be 2-sided, with type I error = 0.05. Interaction tests will generally be done at the 0.10. Statistical significance is determined at a  $\leq$  0.05 alpha level.

### **13.3 Documentation Conventions**

Statistical analyses will be performed using SAS®, version 9.4 or higher (SAS Institute, Cary, NC). Additional statistical software may be used as needed. Where applicable, all the tables and listings will be presented by study randomization arm and overall.

---

 See Appendix 2 for details

### **13.4 Verification of SAS® Codes**

All tables, listings, and graphs will be verified and reviewed before being considered final. The verification process will ensure that the numbers are produced by a statistically valid method and that the execution of the computations is correct. Suitably qualified personnel who have not been previously involved in the production of the original SAS® code will perform the verification procedures. Methods of verification will include independent programming of all analysis datasets and comparison to data listings as specified in the verification plan. Tables will be reviewed for accuracy, consistency with this analysis plan, consistency within tables, and consistency with corresponding output. Once verification is complete, all documentation of the verification process will be filed in a statistical programming documentation as required by the Statistical Standard Operations Procedure (CT Stats SOP ST-S-010, 11.0, 31Jan2017, V.E) of the Duke Clinical Research Institute (DCRI).

### **13.5 Handling of Missing Data**

All efforts will be made to make sure all data needed for the analyses outlined in the SAP are complete. However, it is possible that some data will be missing. Missing data is a common problem in clinical research. It reduces statistical power (the probability that the test will reject the null hypothesis when it is false) and results in biased parameter estimates (Kang, 2013). Outcomes for participants who do not provide data during the 180 day visit will be imputed as failures. Missing heart rate, PGA and KCCQ values will be imputed for the final (180 day) visit using multiple imputation technique if more than 10% of the measures are missing.

It is expected that missing 180 day visit values constitute > 10% of the secondary endpoints (Heart rate, KCCQ and PGA). Thus, multiple imputation (MI) will be performed and presented for the ITT and Treated populations, respectively.

Imputation will be conducted using PROC MI and imputed data analyzed with PROC MIANALYZE in SAS 9.4.

The following variables shall be used in the imputation:

AGE, SEX, RACE, ETHNICITY, WEIGHT, NYHA class, LVEF, and baseline value of the imputed variable) – For NYHA class, WEIGHT and LVEF, baseline values will be used.

RACE shall be recoded to: White, Black and Others (combining American Indian, other, and mixed - as they are of very low frequency)

Results of the imputation shall be presented as the primary result of the secondary endpoints. A total of 25 imputations will be conducted for each imputed value.

Sensitivity analyses will be conducted by analyzing these endpoints with and without imputation.

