## **9.2 Secondary Analyses**

### **1. Heart Rate Assessments**

- a. Change in heart rate from baseline to 180 days will be compared across randomization groups. Change will be calculated as follows: (Baseline heart rate – 180 day heart rate). Comparisons across randomization groups will be performed using a linear model with adjustment for baseline heart rate and beta-blocker use. Randomization groups will be included in the regression model as main effect.

---

 Baseline beta-blocker use will be coded as a “0/1” variable with participants who received beta-blocker coded as “1” and those who did not receive beta-blocker as “0”.

 All change from baseline results presented are calculated similarly.

Heart rate is expected to be lower in the ivabradine arm than the usual care arm.  
Thus, change from baseline is expected to be higher in the ivabradine arm.

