**Model (linear):**

**HR at 180 days = Intercept +  $\beta_1$ \*treatment +  $\beta_2$ \* baseline HR +  $\beta_3$ \* baseline BB use**

**Hypothesis:**

**H0:  $\beta_1=0$**

**H1:  $\beta_1\neq 0$ .**

**The null hypothesis will be rejected if the p-value of the treatment effect is <0.05**

- c. The proportion of participants with heart rate < 70 bpm at 180 days will be evaluated. Differences between the randomization arms will be evaluated using the Chi-square test.
2. Changes in symptoms and quality-of-life from baseline to 180 days as assessed by KCCQ and PGA will be evaluated across randomization groups using a linear model with adjustment for the baseline quality-of-life and beta-blocker use. The differences between the randomization arms will be estimated using point estimates and the associated two-sided 95% confidence intervals

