**Change in PGA at 180 days = Intercept +  $\beta_1$ \*treatment +  $\beta_2$ \* baseline PGA +  $\beta_3$ \* baseline**

**BB use**

**Hypothesis:**

**H0:  $\beta_1=0$**

**H1:  $\beta_1\neq 0$ .**

**The null hypothesis will be rejected if the p-value of the treatment effect is <0.05**

Missing values of 180 day heart rate, KCCQ and PGA will be imputed if missing values

---

 If events are rare, p-value from the Fisher's exact test will be reported.

exceed 10% of the observations (see section 12.5).

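### The multiple-imputation variable list omits randomised arm, so the headline 180-day heart-rate, KCCQ and PGA effects shrink by about the fraction missing

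*SAP*

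**What the plan says.** SAP 13.5 introduces its list with "The following variables shall be used in the imputation" and names "AGE, SEX, RACE, ETHNICITY, WEIGHT, NYHA class, LVEF, and baseline value of the imputed variable". It specifies PROC MI and PROC MIANALYZE with 25 imputations, for both the ITT and the Treated populations. It mentions no step by arm.

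Imputation is triggered when more than 10% of values are missing, and the SAP expects the trigger to be met: "It is expected that missing 180 day visit values constitute > 10% of the secondary endpoints". The imputed analysis then leads: "Results of the imputation shall be presented as the primary result of the secondary endpoints". The unimputed analysis is kept only as a check: "Sensitivity analyses will be conducted by analyzing these endpoints with and without imputation".

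The models in SAP 9.2 all contain arm. For heart rate, "Randomization groups will be included in the regression model as main effect". KCCQ and PGA use a "linear model with adjustment for the baseline quality-of-life and beta-blocker use", again with a treatment term whose coefficient is tested. Baseline beta-blocker use is in every one of these models but is also missing from the list.

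Protocol 10.4 names multiple imputation without giving variables. SAP Appendix 1 only refers back to the missing-data section.

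**The concern.** An imputation model should contain at least the terms of the analysis model, above all the effect being estimated. If arm is left out, participants with missing data are in effect imputed as having no treatment difference. Averaging them with the observed participants pulls the estimated effect towards zero.

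Rubin's rules do not correct for this. The imputation and analysis models disagree, and the pooled standard error then overstates the true sampling variation. The headline result for three secondary endpoints would understate a real effect and carry an interval that is too wide.

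A no-effect assumption can be defended if it is chosen and named. SAP 9.1, 9.3 and 13.5 do code participants without day-180 data as failures for ivabradine use and dose. Nothing comparable is stated for heart rate, KCCQ or PGA. The SAP also does not say whether participants who died before day 180 receive an imputed value for these endpoints.

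**Working it through.** **Inputs from the documents.** KCCQ difference 5 points, SD 16, 450 participants, about 8% missing, two-sided 0.05 (Protocol 10.2); 104 participants enrolled (SAP 2.3); imputation list and 25 imputations (SAP 13.5); analysis models (SAP 9.2).

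**Assumed.** Missing fractions of 20% and 30% (only the 10% floor is documented), baseline to day-180 correlation 0.4, and 10 of 104 participants not on a beta-blocker.

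**The plan's own figure.** 450 × 0.92 = 414, or 207 per arm. A two-sample t-test for 5 points with SD 16 then has 88.9% power, which agrees with the stated figure of about 90%.

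**Formula.** Let d be the true effect, f1 and f0 the missing fractions, and p = 1 − f in each arm. Without arm in the model, missing values in both arms are centred on the pooled observed mean, which lies d·p1/(p1 + p0) above the control mean. With equal arms, the difference after imputation is

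d·[p1 + (f1 − f0)·p1/(p1 + p0)] = d·2·p1·p0/(p1 + p0).

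With f1 = f0 = f this is d(1 − f). For d = 5, that gives 4.5, 4.0 and 3.5 at 10%, 20% and 30%. With 10% and 30% missing in the two arms, the retained fraction is 2 × 0.9 × 0.7/1.6 = 0.79.

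**Simulation.** N = 104, true difference 5, values missing completely at random, Bayesian normal-regression imputation from all listed variables, Rubin's rules, and a linear model on arm, baseline and beta-blocker use; 7,000 replicates per cell, Monte Carlo error about 0.04. Ranges for power and null rejection are with and without the small-sample degrees-of-freedom correction.

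| | 10% missing | 20% | 30% |
|---|---|---|---|
| Mean estimate, list as written | 4.6 | 4.0 | 3.5 |
| List plus beta-blocker use only | 4.5 | 4.0 | 3.5 |
| List plus arm only | 5.0 | 5.1 | 5.0 |
| List plus both | 5.0 | 5.1 | 5.0 |
| No imputation | 5.0 | 5.1 | 5.0 |
| As written: reported SE | 3.10 | 3.32 | 3.52 |
| As written: true sampling SD | 2.80 | 2.61 | 2.52 |
| As written: SE excess | 11% | 27% | 40% |
| Power, as written | 28–29% | 16–17% | 8% |
| Power, plus both | 36–37% | 31–32% | 26–27% |
| Null rejection, as written | 3.0–3.2% | 1.4% | 0.5–0.6% |

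With both variables added, null rejection is 4.7–5.2% and the reported standard error is within 0–3% of the truth. Omitting arm alone causes the shrinkage.

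**Robustness.**
- With correlation 0.5 instead of 0.4, the list as written gives 4.50, 4.02 and 3.49. Power at 20% missing is 22% as written and 37% with both added. The shrinkage does not depend on the correlation; the power figures do.
- When missingness depends on baseline and arm (about 10%, 19% and 29% missing), the retained fractions are 0.90, 0.80 and 0.70.
- For a seven-category PGA-type outcome, the retained fractions are 0.90, 0.80 and 0.70.
- The ratio does not depend on scale, so it applies to heart rate too, for which the documents give no planning values.

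**When the unimputed analysis also fails.** Let dropout of 10% and 30% be crossed between arms and NYHA groups (20% missing overall), with the NYHA-like covariate worth an assumed 4, 8 or 12 points. The unimputed estimate is then 4.5, 4.0 and 3.5; the list as written gives 3.9 each time; the list plus both gives 5.0 each time.

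**Deaths.** Protocol 1.1 cites 20–30% one-year mortality. At constant hazard, 1 − 0.80^(180/365) = 10.4% and 1 − 0.70^(180/365) = 16.1% by day 180, about 11 to 17 of 104. With 10% dead and 10% otherwise missing, the estimate is 4.0 as written, 4.5 as written with deaths left out, and 5.0 with both variables added and deaths left out. With 16% dead and 10% otherwise missing, these are 3.7, 4.4 and 5.0. Leaving deaths out does not by itself repair the omission.

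**The case against.** - **The plan already contains the check.** The unimputed analysis is unbiased in the main scenarios and will be reported. The scenario that breaks it is constructed, and nothing in the documents points to that dropout pattern. This stands in part: a reader comparing the two results would see the gap. The shrunken result is still the one that leads.
- **The harm is small and conservative.** At 10% missing the loss is about 0.5 points against a standard error near 3, with no excess false positives. This stands. It is also true that the list as written has the lower mean squared error at this sample size: √(0.45² + 2.80²) ≈ 2.8 at 10% missing, against an SD of about 3.1 with both variables added. That gain comes only from pulling the estimate towards zero and does not make the interval or test valid.
- **Five points is generous.** Protocol 10.2 plans 50% against 35% ivabradine use. If benefit came only through use at day 180, a 10-point benefit per user would give 10 × 0.15 = 1.5 points between arms, and a 10–30% loss would be 0.15–0.45 points. The absolute loss would then be small, but the proportional loss is unchanged.
- **Heart rate may be less affected.** SAP 13.1 and Appendix 1 allow vital-sign or medical-record values and visits within 60 days of the window, so fewer heart rates may be missing. This is fair, although SAP 13.5 expects more than 10% missing for all three endpoints.
- **Something unseen may settle it.** The title of Addendum 2 implies an Addendum 1, which is not in the copy reviewed, and a PROC MI run by arm is not expressly excluded. The point therefore concerns the list as written, not what was run.
- **The mortality range is general.** It may overstate deaths in a clinically stable, selected population. The death figures are illustrative only.

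**Conclusion.** The concern holds. As written, SAP 13.5 imputes three secondary endpoints from a model without the effect under test and ranks that result first. Under missing at random with similar missingness in the two arms, the estimate keeps about (1 − f) of the true effect. With unequal missingness it keeps the harmonic mean of the two observed fractions. At the documented floor of 10%, the loss is about a tenth of the effect; at an assumed 20% or 30%, it is a fifth or nearly a third, with a standard error 27% or 40% too large.

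The shrinkage ratio is secure. The power and standard-error figures depend on the assumed baseline correlation. The proportion with heart rate below 70 bpm is a separate chi-square analysis and was not simulated. The primary endpoint is unaffected, and there is no inflation of false positives. This should be fixed, but it does not threaten the trial's main conclusion.

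**What to change.** In SAP 13.5:

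1. Add randomised arm and baseline beta-blocker use to the PROC MI variable list. Imputing separately by arm is an alternative in the ITT population but may be too thin in the Treated population. Arm corrects the shrinkage; beta-blocker use makes the imputation model contain every analysis-model term.
2. State that participants who died before day 180 are not given an imputed value under this model, or are handled in a separate named analysis.
3. If a no-effect assumption for missing participants is wanted, make it a named sensitivity analysis, for example reference-based imputation.

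Addendum 2 shows that the database has been locked and treatment unblinded, and SAP 1 requires an amendment for substantive changes. The amendment should therefore give its date relative to unblinding and say which result leads. The result under the present list should be reported beside the new one.

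The cost is two variables already collected, a sentence on deaths, a rerun of the imputation and the amendment. No new data are needed. The drawback is that if missing participants truly have no treatment effect, the corrected estimate would be too large (about 5.0 against a diluted 4.5, 4.0 or 3.5); the sensitivity analysis in item 3 addresses that. The collected week-6 values remain outside the imputation model, so this change removes the bias described here but does not make the imputation complete in every respect.
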